7.4 Baseline evaluations (Day -7 to Day -1)

The results from the Screening visit evaluations will be reviewed to determine if the patient continues to meet the eligibility requirements as specified in the protocol. Patients who have signed the informed consent form and meet all the entry criteria (see Inclusion/Exclusion Criteria [Section 5.2](#) and [Section 5.3](#)) will be enrolled in the study. Procedures for the Baseline visit may be conducted over 1 to 7 days as needed. Blood samples for hematology and serum chemistry should be performed at least 4 days prior to the intended Study Day 1, in order to allow ample time for results to be returned before administration of INC424. All evaluations should be recorded in the source documents and promptly entered in the eCRF.

The following procedures will be performed at the Baseline visit and prior to enrollment for all patients:

- Confirm that the patient continues to meet all relevant inclusion and exclusion criteria, considering evaluations occurring at screening and baseline.
- Update medication history; confirm all drugs used to treat underlying PMF, PPV MF, or PET-MF.
- Record any concomitant medications.
- Update transfusion history status.

- Blood sampling for serum chemistry tests, hematology, and coagulation (PT, PTT, or INR) (see [Appendix III](#)). ECOG status must be 0, 1, or 2 ([Appendix IV](#)).
- FACT-Lym version 4 ([Appendix VII](#)) and FACIT-Fatigue Subscale ([Appendix VIII](#)).
- Medical resource utilization:
 - Number and duration of hospitalization in the past 3 month
 - Number of emergency room visits in the past 3 months
 - Number of general practitioner, specialist, urgent care visits in the past 3 months.
 - Number of transfusions in the past 3 months and baseline transfusion dependency status
 - Number of splenic irradiation treatments in the past 3 months.
- Targeted physical examination including body weight and measurement of spleen by palpation ([Section 8.2.3](#)).
- Record adverse events.
- Vital signs (blood pressure, heart rate, respiratory rate and body temperature) to be performed in a sitting position after 5 minutes of rest.
- 12-lead ECG performed in the recumbent position after 5 min of rest, ONLY if not conducted during the Screening Visit, or if conducted and found to include an abnormality deemed clinically significant.
- Patients will be instructed to discontinue all drugs to treat PMF, PPV MF, or PET-MF on the morning of the Day 1 Visit.

7.4.1 Combining Screening and Baseline Visits into 1 Visit

It is permissible to combine the Screening and Baseline visits if necessary, provided all results are available prior to the first dose of INC424

If Screening visit and Baseline visits overlap (-7 to -1)

- a. Enter information as required
- b. Information requested at both Screening visit and Baseline visit should be entered only once in Screening visit pages

7.5 On treatment evaluations

On-treatment evaluations are scheduled for Study Visits at Day 1, and at the end of Weeks 4, 8, 12, and every 12 weeks thereafter. If it is determined at any Study Visit that the patient will discontinue study drug that day, then that study visit will be the End of Study Visit, and the End of Study Visit procedures will be followed.

After 4 weeks of treatment (Week 4 Visit), patients may have the dose of INC424 increased because of inadequate responses. At this visit or anytime during the study, the dose may be adjusted for safety, following the guidelines described in [Section 6.2](#), Dose Modifications. The individual study visit descriptions describe activities that must occur to support and document these dose changes.

This study schedule is designed to closely monitor any drug related adverse events associated with INC424. If, at any time during the study, a patient experiences unexpected signs or

symptoms, additional safety evaluations should be conducted at a regular Study Visit or unscheduled visit. For example, weekly monitoring is advised for patients with platelet counts < 100,000/ μ L or neutrophils < 1000/ μ L, and at least twice -weekly for platelets < 50,000/ μ L or neutrophils < 500/ μ L. Additionally, x-ray examination of the thorax, echocardiography, and pulmonary function testing and/or arterial blood gas analysis should be considered in patients developing new or worsening cardiopulmonary symptoms including cough, shortness of breath, exercise intolerance or peripheral edema.

Women of childbearing potential will be assessed for pregnancy status, either by serum or urine pregnancy tests, prior to starting treatment with INC424 only (see [Section 5.2](#)). If local requirements mandate more frequent testing, applicable sites will conduct monthly testing.

See [Section 6.2.2](#) and [Section 6.2.6](#) for criteria for mandatory reduction, interruption, or discontinuation of study drug based upon results of safety monitoring.

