3.3.3 Quality of Life

(See [Table 7-1](#) for assessments)

- Change in ECOG performance status from Baseline to each visit where the variable is measured.
- Changes in Functional Assessment of Cancer Therapy for patients with Lymphoma (FACT-Lym) version 4 from Baseline to each visit where measured ([Appendix VII](#)).
- Change in the Functional Assessment of Chronic Illness Therapy (FACIT) Fatigue Scale from Baseline to each visit where measured (See [Appendix VIII](#)).

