7.6 End of treatment visit, including premature withdrawal and study discontinuation visit

Patients who discontinue study treatment before the end of the study should be scheduled for a visit as soon as possible, at which time all of the assessments listed for the End of Treatment (EOT) visit will be performed. The appropriate eCRF page should be completed, giving the date and reason for stopping the study treatment. At a minimum, all patients who discontinue study treatment, including those who refuse to return for a final visit, will be contacted for safety evaluations during the 28 days following the last dose of study treatment.

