7.6.2 End of treatment evaluations

7.6.2.1 End of study or early termination visit

The End of Study or Early Termination Visit constitutes the final study visit where study drug has been taken. An End of Study Visit may occur with a planned discontinuation for any reason (e.g., at Week 20, it is determined that patient will participate in the study only 1 more month; therefore, the Week 24 Visit will become the End of Study Visit).

The following procedures will be performed and all observations will be recorded in the eCRF:

- Review of concomitant medications.
- Update transfusion history status.
- A targeted physical examination will be performed, including body weight and measurement of spleen by palpation ([Section 8.2.3](#)).
- Vital signs (blood pressure, heart rate, respiratory rate and body temperature) to be performed in a sitting position after 5 minutes of rest.
- Blood sampling for serum chemistry tests, hematology (see [Appendix III](#)).
- Determination of ECOG performance status (see [Appendix IV](#)).
- Drug accountability assessment (see [Section 6.5.4](#)).
- Record adverse events.
- Document the dose the patient was on at the time of study discontinuation.
- Patients will be asked to return to the clinic between 28 and 37 days later for a final Follow-up Visit.
- The sponsor (Novartis Pharmaceuticals) will be notified of the patient withdrawal.

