8.3.3 Resource utilization

Medical resource utilization will be captured at each visit out to 48 weeks. Data collection will include medical resources utilized since the last visit. MRU includes office visits (general practitioner and specialist visits), procedures/treatments, emergency room visits, urgent care visits, hospitalizations, transfusions, splenectomy, splenic radiation and changes in concomitant medications.

9 Safety monitoring and reporting

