3.4.4 Analysis of patient reported outcomes

For the analysis of quality of life assessments/patient reported outcomes (PRO), the scoring of the questionnaires will be handled as specified by the instrument developers.

To assess rate of missing data, a table of completion rates for each questionnaire at each scheduled assessment will be created. The table will include number of patients eligible for PRO assessment and number of patients with complete PRO assessment data, completion will be defined by each instruments scoring guidelines.

Change in individual scores/scales from baseline will be summarized descriptively at each visit. For FACT-Lymphoma scores, repeated measures analysis will also be used.

Change in ECOG Performance Status

The ECOG performance score will be summarized descriptively by visit. The summary will include the number and percent of patients at each reported value. A shift table including the number and percent of patients will also be produced by visit of baseline vs. post-baseline scores.

Change in FACT-Lym scores

The FACT-Lym questionnaire consists of a total of 42 questions contributing to 5 subscales (i.e., physical well-being, social/family well-being, emotional well-being, functional well-being and lymphoma subscale) which in turn contribute to three total sum scores, namely

FACT-Lym Trial Outcome Index (TOI), FACT-General (FACT-G) total score and FACT-Lym total score. More details on the questionnaire and derivation of the score can be found in Section 16.1.9.

Data from FACT-Lymphoma scores will be analyzed in the three sum scores and one subscale LymS. Change and percent change from baseline to each scheduled visit when the FACT-Lymphoma scores were collected will be calculated. The scores will be summarized descriptively by visit. The change from baseline score at each time point will be estimated by using repeated measurement analysis for patients with at least one post-baseline scale score. Patients without baseline value will not be considered in the analysis and baseline is the data collected from the last visit prior to or at Day1.

Time on treatment time will be treated as a discrete variable to allow for a nonlinear relationship between PRO scores and time. Time, DIPSS status and baseline score (as a covariate) will be included in the model as fixed effects, while the patient-specific intercept will be included as a random effect.

DIPSS status will be calculated as per the criteria given in section 3.11.3

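### For patients who stop drug by Week 48, the End of Study visit has no FACT-Lym, FACIT-Fatigue or MRU contact items, so the last quality-of-life and resource-use data can be lost

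*Protocol*

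**What the plan says.** Protocol Section 7.5 covers the case where it is decided at a study visit that drug stops that day: "then that study visit will be the End of Study Visit, and the End of Study Visit procedures will be followed". SAP Section 1.1 repeats the rule. Section 7.6.2.1 gives an example in which a scheduled visit is converted: "therefore, the Week 24 Visit will become the End of Study Visit". Section 7.6 calls in patients who stop early for a visit "at which time all of the assessments listed for the End of Treatment (EOT) visit will be performed".

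The End of Study list in 7.6.2.1 opens with "The following procedures will be performed and all observations will be recorded in the eCRF". It includes concomitant medications, transfusion history, adverse events and "Determination of ECOG performance status". It does not include FACT-Lym, FACIT-Fatigue, or the MRU counts of hospitalisations and of emergency, urgent-care, general practitioner and specialist visits. The Follow-up list (7.6.3.1) does not include them either.

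Section 8.3.3 points the other way for MRU: "Medical resource utilization will be captured at each visit out to 48 weeks", covering use since the last visit.

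On analysis, SAP 3.4.4 states "Change in individual scores/scales from baseline will be summarized descriptively at each visit". SAP 3.4.4.1 allows no imputation. SAP 3.6 summarises resource use by quarter, with no rule for a patient who stops partway through one.

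**The concern.** Quality of life and MRU are two of the three secondary objectives (Protocol 3.2). Progression and unacceptable toxicity are among the listed reasons for stopping (4.1). If scores and resource use nearest to stopping are the ones not collected, by-visit score summaries lean towards patients well enough to continue. Resource use just before stopping, a period when admissions are plausible, also stays out of the MRU tables. For those stops, both effects tend to make the results look better. In a single-arm descriptive study no control arm shares the same loss, so the summaries would have to be read with that in mind.

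**Working it through.** The documents give no figure on this point to reproduce. The check compares the schedules and then shows the possible scale.

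**1. Where the items are scheduled (Table 7-1 and the visit lists)**

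| Item | Scheduled | End of Study / EOT | Follow-up |
|---|---|---|---|
| FACT-Lym, FACIT-Fatigue | Baseline, Weeks 4, 12, 24, 48 | no | no |
| MRU | Baseline, Weeks 4, 8, 12, 24, 36, 48 | no | no |
| ECOG | Every clinic visit except Day 1 | yes | no |
| Transfusion history, concomitant medications | All visits | yes | yes |

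Section 8.2.2 asks for the usual assessments at withdrawal but covers only safety assessments, so it does not restore the missing items. Week 24, the visit used as the example in 7.6.2.1, is one at which both questionnaires and MRU are due.

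**2. Length of the unobserved final stretch**

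This is at most the gap between consecutive scheduled assessments:

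- FACT-Lym and FACIT-Fatigue: 4 − 0 = 4, 12 − 4 = 8, 24 − 12 = 12 and 48 − 24 = 24 weeks.
- MRU: 4, 4 and 4 weeks up to Week 12, then 12, 12 and 12 weeks.

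The MRU gaps assume recall since the last visit, as in 8.3.3. The visit lists for Weeks 24, 36 and 48 ask only about the past month. With a month taken as 4 weeks (SAP 2.3), 12 − 4 = 8 weeks of each such interval go uncovered even in patients who continue. The recall period is a second inconsistency to settle. Under either wording, an admission shortly before stopping falls inside the recall window but is not asked about at End of Study.

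**3. Number of patients**

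Patients affected = 2238 enrolled × share stopping by Week 48. The share is an assumption, because the documents give none for this trial.

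| Assumed share | Calculation | Patients |
|---|---|---|
| 5% | 0.05 × 2238 | about 112 |
| 11% | 0.11 × 2238 | about 246 |
| 20% | 0.20 × 2238 | about 448 |
| 30% | 0.30 × 2238 | about 671 |

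The 11% is the adverse-event discontinuation rate that Protocol 1.3.5 quotes for ruxolitinib in the Phase III trials. It is one point in the range, not an estimate for this study. These are upper counts of patients with a gap: some will have completed that day's questionnaires, and FACT-Lym and FACIT-Fatigue are not due at Weeks 8 and 36 for anyone.

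**4. Who is not affected**

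Stops after Week 48 lose nothing on these items, since nobody has them scheduled after that. Earlier scheduled values are kept for every patient.

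**The case against.** The strongest reply has five parts.

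- **Same-day decisions.** At Weeks 4, 12, 24 and 48 the questionnaires are to be completed before the examination. If stopping is decided after it, the forms may already be filled in, and Section 7.5 does not say that items already due are cancelled. SAP 3.4.4.2 uses all scheduled and unscheduled assessments. This stands: the loss of a score is clear only when stopping is decided beforehand or between visits.
- **MRU is contested, not omitted by choice.** Section 8.3.3 requires it at each visit to Week 48. This stands: for MRU the protocol contradicts itself, and the passages must be reconciled.
- **Other data remain.** ECOG is itself a quality-of-life endpoint (3.3.3: "Change in ECOG performance status from Baseline to each visit where the variable is measured") and is kept at End of Study, as are transfusions and concomitant medications. Inpatient hospitalisation is an SAE criterion (9.2.1), and SAEs are reported until at least 28 days after stopping (9.2.2). This stands in large part. However, progression and leukemic transformation are exempt from SAE reporting, general practitioner, specialist and urgent-care counts have no other source, and the SAP does not link SAE admissions to the MRU tables.
- **The SAP already does something.** It plans completion rates per questionnaire and visit and a repeated-measures model with a patient random intercept for FACT-Lym. These help, but completion is not split by stopping status, and a model cannot use a score that was never collected.
- **Not all stops are informative.** Stopping because the drug became commercially available need not be related to health. This stands.

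**Conclusion.** The point holds for stops on or before Week 48 and for FACT-Lym, FACIT-Fatigue and the MRU hospitalisation and visit items. The last on-drug score can be lost, and resource use since the last MRU visit does not enter the MRU endpoint. Where stopping is for progression or toxicity, the effect tends to be favourable to the drug. Its size is unknown: about 112 to 671 patients if 5% to 30% stop by Week 48, which is an assumed range.

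A reader might infer three stronger things, and the documents support none of them.

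- **Quality of life and resource use are missing by design in everyone who stops.** ECOG, transfusions and concomitant medications are collected, later stops are unaffected, and 8.3.3 contradicts the omission of MRU.
- **The admission that led to stopping is lost to the trial.** It is absent from the MRU tables but would normally be in the SAE data, apart from exempt progression and the other exceptions in 9.2.1.
- **A number of uncounted admissions can be calculated.** That would need this trial's stopping rate by Week 48, the share of stoppers admitted in the final stretch and an agreed recall period. The documents supply none of the three.

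**What to change.** 1. **Protocol 7.5, 7.6.2.1 and Table 7-1.** Require FACT-Lym, FACIT-Fatigue and MRU at the End of Study/EOT visit when it falls on or before Week 48. Set MRU recall to the time since the last visit, in line with 8.3.3, and bring the past-month wording of the visit lists into agreement. The cost is a few minutes of questionnaire at a visit that already takes place. Recruitment ended on 31 Dec 2014, so the last patients reach Week 48 around the end of 2015 and the change may reach few of them.

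2. **SAP 3.6 and 3.4.4.** Report hospitalisations and visits per patient-time actually covered by MRU, and questionnaire completion by stopping status. This costs analysis time only.

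3. **SAP 3.6, sensitivity analysis only.** Count hospitalisation SAEs for all patients over the same on-treatment window to Week 48, and state that progression-related admissions exempt from SAE reporting are missed. Using SAE data to fill the gap only in patients who stop, or extending it into the 28 days after the last dose, would add a second data source and off-drug time mainly for stoppers and so introduce a new bias. The documents do not show that SAE forms hold admission and discharge dates, so this analysis should be limited to counts unless that is confirmed.

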7.5.1 On treatment evaluation requirements

[figure not shown]
7.5.1.1 Day 1

The Day 1 visit may occur as soon all Baseline evaluations have been completed, and the laboratory data (including platelet count) from the Baseline Visit are available. The following procedures will be performed and all observations will be recorded in the eCRF:

- Record any concomitant medications.
- Determine the date and time of last administration of prior therapy (if any) for treatment of PMF, PPV MF, or PET-MF.
- Update transfusion history status.
- Administer the morning dose of INC424, and monitor the patient for adverse events/tolerability.
- Dispense study drug for the first 28 days (plus overage) along with dosing instructions.
 - The importance of compliance will be reviewed with the patient.
 - The patient will be educated on medications and food that should be avoided while taking INC424.
 - The patient and/or family members are to be instructed to telephone the study site with any changes in mental or physical status or questions about INC424, and also to return all unused INC424.
- Patients will be instructed to call the investigator or designated research staff if they experience any unexpected and unfavorable signs and/or symptoms. These adverse events will be recorded on the eCRF.

7.5.1.2 Week 1 through Week 4

Patients will self-administer INC424 BID as instructed, morning and evening (at approximately 12-hour intervals), in an outpatient setting. Patients will call the investigator or designated research staff if they experience any unexpected and unfavorable signs and/or symptoms.

Patient may attend the study clinic up to 3 days prior to week 4 to provide blood samples for serum chemistry tests and hematology ([Appendix III](#)). The laboratory results should be available for interpretation and potential dose modification on the Week 4 Study Visit.

7.5.1.3 Week 4 (\pm 7 days)

The following procedures will be performed and all observations will be recorded in the eCRF:

- Review of concomitant medications.
- Update transfusion history status.
- Blood sampling for serum chemistry tests, hematology, and optional coagulation (PT, PTT, or INR) (see [Appendix III](#)).
- A targeted physical examination will be performed, including body weight and measurement of spleen by palpation ([Section 8.2.3](#)).
- provided **all** requirements for dose at week 4 according to starting INC424 dose as follows:
 - By 5 mg BID if palpable spleen length reduced by less than 40% relative to Baseline, provided **all** requirements for dose increase are met (see [Section 6.2.1.1](#)).
 - The dose increase may only be an increase of 5 mg o.d. (e.g., for those patients starting INC 424 at 5 mg PO BID to 5 mg QAM and 10 mg QPM).
- All changes in dose, including rationale for dose increase, should be recorded in the eCRF.
- The dose of INC424 may need to be decreased or interrupted because of low platelet counts or ANC levels (see [Section 6.2.2](#)).
- Vital signs (blood pressure, heart rate, respiratory rate and body temperature) to be performed in a sitting position after 5 minutes of rest.
- Determination of ECOG performance status (see [Appendix IV](#)).
- Complete FACT-Lym version 4 ([Appendix VII](#)) and FACIT-Fatigue Subscale (prior to examination) ([Appendix VIII](#)).
- Medical Resource Utilization in the past month:
 - Number and duration of each hospitalization.
 - Number of emergency room visits.
 - Number of urgent care visits.
 - Number of additional general practitioner and specialist office visits.
 - Number of transfusions and transfusion dependency status.
 - Splenectomy or splenic irradiation.
- 12-lead ECG performed in the recumbent position after 5 minutes of rest.
- Drug accountability assessment (see [Section 6.5.4](#)).
- Assessment of patient compliance.
- Record adverse events.
- Study drug for the next 28 days (plus overage) will be dispensed along with dosing instructions.
- Patients will be instructed to call the investigator or designated research staff if they experience any unexpected and unfavorable signs and/or symptoms.

7.5.1.4 Week 4 through Week 8

Patients will self-administer INC424 BID as instructed, morning and evening in an outpatient setting. Patients will call the investigator or designated research staff if they experience any unexpected and unfavorable signs and/or symptoms.

[figure not shown]
7.5.1.5 Week 8 (\pm 7 days)

The following procedures will be performed and all observations will be recorded in the eCRF:

- Review of concomitant medications.
- Update transfusion history status.
- A targeted physical examination will be performed, including body weight and measurement of spleen by palpation ([Section 8.2.3](#)).
- Vital signs (blood pressure, heart rate, respiratory rate and body temperature) to be performed in a sitting position after 5 minutes of rest.
- Blood sampling for serum chemistry tests, hematology, and optional coagulation (PT, PTT, or INR) (see [Appendix III](#)).
- Determination of ECOG performance status (see [Appendix IV](#)).
- MRU in the past month:
 - Number and duration of each hospitalization.
 - Number of emergency room visits.
 - Number of urgent care visits.
 - Number of additional general practitioner and specialist office visits.
 - Number of transfusions and transfusion dependency status.
 - Splenectomy or splenic irradiation.
- Document new (changed) or ongoing dose information for INC424. Dose changes that are necessary between study visits will be communicated immediately and directly to the patient by telephone; the communication will be documented in the source documents.
- Drug accountability assessment (see [Section 6.5.4](#)).
- Assess patient compliance.
- Record adverse events.
- Study drug for the next 28 days (plus overage) will be dispensed along with dosing instructions.
- Patients will be instructed to call the investigator or designated research staff if they experience any signs and/or symptoms. These adverse events will be recorded on the eCRF. Patients will be reminded to bring the study drug to the clinic with them.

7.5.1.6 Week 8 through Week 12

Patients will self-administer INC424 BID as instructed, morning and evening in an outpatient setting. Patients will call the investigator or designated research staff if they experience any unexpected and unfavorable signs and/or symptoms.

